6.2 IMPORTANT PROTOCOL DEVIATIONS

Data discrepancies and deviations from the CTP will be identified for all subjects enrolled in this trial.

Consistency check listings (for identification of deviations from time windows) and a list of protocol deviations (e.g. deviations in drug administration, in blood sampling times, etc.) will be provided to be discussed at the medical quality review meeting, the blinded report planning and database lock meeting (RPM/DBLM). At this meeting, it will be decided whether a discrepant data value can be used in analyses or whether it must be corrected in the clinical database. Each protocol deviation must be assessed to determine whether it is an important protocol deviation (iPD). For definition of iPDs, and for the process of identification of these, refer to the Boehringer Ingelheim (BI) SOP "Integrated Quality and Risk Management Process" ([2](#)).

If any iPDs are identified, they are to be summarised into categories and will be captured in the RPM/DBLM minutes via an accompanying excel spreadsheet. Categories which are considered to be iPDs in this trial are defined in the integrated quality and risk management plan (IQRMP). If the data show other iPDs, the definition in the IQRMP will be supplemented accordingly by the time of the RPM/DBLM.

iPDs will be summarised and listed.

6.3 SUBJECT SETS ANALYSED

All entered subjects who received study medication will be included in the safety analysis and in the PK analysis depending on the availability of measurement values, and on their adherence to the CTP.

The following subject sets will be defined for statistical analysis:

- Treated set (TS):
This subject set includes all subjects who received at least one dose of study drug. This is the full analysis set population in the sense of ICH-E9 ([1](#)). It will be used for analysis of safety, demographic data and baseline characteristics.
- Pharmacokinetic parameter set (PKS):
This subject set includes all subjects in the TS who provide at least one primary PK

parameter that was not excluded because of protocol deviations relevant to the statistical evaluation of PK endpoints as defined in Section 7.3 of the CTP.

The discussion of all exceptional cases and problems and the decisions on the allocation of subjects to analysis sets will be made at latest at the RPM/DBLM.

Table 6.3: 1 Subject sets analysed

Class of endpoint	Subject set	
	TS	PKS
Disposition	X	
Exposure	X	
iPDs	X	
Demographic/baseline endpoints	X	
Safety parameters	X	
Primary PK endpoint		X
Further PK endpoints		X

6.5 POOLING OF CENTRES

This section is not applicable, because the study was performed in only one centre.

6.6 HANDLING OF MISSING DATA AND OUTLIERS

Data of screened subjects who were withdrawn from the trial prior to first administration of any study drug will not be reported in the CTR.

Data of subjects who failed to complete all periods of the study (dropouts or withdrawals) will be reported in the CTR as far as their data are available. All withdrawals will be documented and the reason for withdrawal recorded in the CTR.

CTP: *It is not planned to impute missing values for safety parameters.*

The only exceptions where imputation might be necessary for safety evaluation are AE dates. Missing or incomplete AE dates are imputed according to BI standards (3).

Missing data and outliers of PK data are handled according to BI standards (4) and (6).

6.7 BASELINE, TIME WINDOWS AND CALCULATED VISITS

The last non-missing value determined prior to the first study drug administration will be defined as baseline.

Time windows are defined in Section 6.1 of the CTP. Adherence to time windows will be checked at the RPM/DBLM.

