Visit	Day	Planned time (relative to first drug administration) [h:min]	Approximate clock time of actual day [h:min]	Event and comment	Safety laboratory	PK plasma BI 730357	PK plasma [C-14]BI 730357 BS	12-lead ECG	Vital signs (BP, PR)	Local tolerability assessment	Questioning for AEs and concomitant therapy ⁷
1	-21 to -2			Screening (SCR) ¹	x						
2	-1	-18:00	14:00	Admission to trial site	x ⁵			x	x		
		-14:00	18:00	Dinner							
		-10:30	21:30	Light supper (voluntary) ⁸							
	1	-2:00	06:00			x ^{2,3}	x ³	x ³	x ³		
		0:00	08:00	Drug administration (50 mg BI 730357 as tablet, oral)							
		1:00	09:00			x					
		1:15	09:15	Start of IV infusion containing BI 730357 BS (C-14)							
		1:20	09:20				x				
		1:25	09:25				x				
		1:30	09:30	Stop of IV infusion		x	x				
		1:45	09:45			x				x	
		2:00	10:00	240 mL fluid intake		x	x	x			
		2:30	10:30			x	x				
		3:30	11:30			x	x				
		4:00	12:00	240 mL fluid intake				x	x		
		5:00	13:00	Lunch ⁴		x	x				
		7:00	15:00			x	x				
		11:00	19:00	Dinner							
		12:00	20:00			x	x				
	2	24:00	08:00	Breakfast (voluntary) ⁴ , discharge from trial site	x	x	x	x	x	x	
	4	72:00	08:00	Ambulatory visit ⁹		x	x				
	6	120:00	08:00	Ambulatory visit ⁹	x	x	x				
	8	168:00	08:00	Ambulatory visit ⁹		x	x				
3	9 to 15			End-of-trial (EoTrial) examination ⁶	x			x	x		x

1. Subject must be informed and written informed consent obtained prior to starting any screening procedures. Screening procedures include physical examination, check of vital signs, ECG, safety laboratory (including drug screening), demographics (including determination of body height and weight, smoking status and alcohol history), relevant medical history, concomitant therapy and review of inclusion/exclusion criteria.
2. Including pharmacogenomics sample
3. The time is approximate; the procedure is to be performed and completed within 3 h prior to drug administration.
4. If several actions are indicated at the same time point, the intake of meals will be the last action.
5. Safety lab including urine drug and alcohol screening.
6. At the end-of-trial visit, the EoTrial examination includes physical examination, vital signs, ECG, safety laboratory, recording of AEs and concomitant therapies.
7. AEs and concomitant therapies will be recorded throughout the trial; during in-house days subjects will be specifically asked for twice daily.

Proprietary confidential information © 2018 Boehringer Ingelheim International GmbH or one or more of its affiliated companies

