3.3.3 Exclusion criteria

Subjects will not be allowed to participate, if any of the following general criteria apply:

1. Any finding in the medical examination (including BP, PR or ECG) deviating from normal and assessed as clinically relevant by the investigator
2. Repeated measurement of systolic blood pressure outside the range of 90 to 139 mmHg, diastolic blood pressure outside the range of 45 to 89 mmHg, or pulse rate outside the range of 40 to 100 bpm
3. Any laboratory value outside the reference range that the investigator considers to be of clinical relevance
4. Any evidence of a concomitant disease assessed as clinically relevant by the investigator
5. Clinically significant gastrointestinal (including known or suspected inflammatory bowel disease), hepatic, renal, respiratory, cardiovascular, metabolic, immunological or hormonal disorders
6. Cholecystectomy or other surgery of the gastrointestinal tract that could interfere with the pharmacokinetics of the trial medication (except appendectomy or simple hernia repair)
7. Diseases of the central nervous system (including but not limited to any kind of seizures or stroke), and other relevant neurological or psychiatric disorders
8. History of relevant orthostatic hypotension, fainting spells, or blackouts
9. Chronic or relevant acute infections
10. History of relevant allergy or hypersensitivity (including allergy to the trial medication or its excipients)
11. Use of drugs within 30 days of planned administration of trial medication that might reasonably influence the results of the trial (including drugs that cause QT/QTc interval prolongation)
12. Intake of an investigational drug in another clinical trial within 60 days of planned administration of investigational drug in the current trial, or concurrent participation in another clinical trial in which investigational drug is administered
13. Smoker (more than 5 cigarettes or 1 cigar or 1 pipe per day)
14. Inability to refrain from smoking on specified trial days
15. Average intake of more than 24 units of alcohol per week (1 unit of alcohol equals approximately 250 mL of beer, 100 mL of wine or 35 mL of spirits)
16. Drug abuse or positive drug screening
17. Blood donation or loss of more than 100 mL within 60 days of planned administration of trial medication or intended blood donation during the trial. Donation or loss of more than 1.5 litres of blood in the 10 months prior to planned administration of trial medication.

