5.2.3 Safety laboratory parameters

For the assessment of laboratory parameters, blood and urine samples will be collected by the trial site at the times indicated in the [Flow Chart](#) after the subjects have fasted for at least 4 h (at admission on Day -1, only) or at least 10 h (all other time points). Subjects do not need to have fasted for drug screening and for infectious serology at the discretion of the investigator. Overnight fasting is not required at the discretion of the investigator or designee for re-tests.

The parameters that will be determined are listed in Tables [5.2.3: 1](#) and [5.2.3: 2](#). Reference ranges will be provided in the ISF, Section 10.

Manual differential white blood cell count or urine sediment examinations will only be performed if there is an abnormality in the automatic blood cell count or in the urinalysis, respectively.

Proprietary confidential information © 2018 Boehringer Ingelheim International GmbH or one or more of its affiliated companies

Table 5.2.3: 1

Routine laboratory tests

Functional lab group	BI test name [comment/abbreviation]	A	B
Haematology	Haematocrit Haemoglobin Red Blood Cell Count/Erythrocytes Reticulocytes, absol. White Blood Cells/Leucocytes Platelet Count/Thrombocytes (quant)	X X X X X X	X X X X X X
Automatic WBC differential, relative	Neutrophils/Leukocytes; Eosinophils/Leukocytes; Basophils/Leukocytes; Monocytes/Leukocytes; Lymphocytes/Leukocytes	X	X
Automatic WBC differential, absolute	Neutrophil, absol.; Eosinophils, absol.; Basophils, absol.; Monocytes, absol.; Lymphocytes, absol.	X	X
Manual differential WBC (if automatic differential WBC is abnormal)	Neut. Poly (segs); Neut. Poly (segs), absol.; Neutrophils Bands; Neutrophils Bands, absol.; Eosinophils/Leukocytes; Eosinophils, absol.; Basophils/ Leukocytes; Basophils, absol.; Monocytes/ Leukocytes; Monocytes, absol.; Lymphocytes/Leukocytes; Lymphocytes, absol.		
Coagulation	Activated Partial Thromboplastin Time INR (International Normalization Ratio)	X X	X X
Enzymes	AST [Aspartate transaminase] /GOT, SGOT ALT [Alanine transaminase] /GPT, SGPT Alkaline Phosphatase Gamma-Glutamyl Transferase Creatine Kinase [CK] Creatine Kinase Isoenzyme MB [only if CK is elevated] Lactic Dehydrogenase Lipase Amylase (total)	X X X X X X X X X X	X X X X X X X X X
Hormones	Thyroid Stimulating Hormone	X	--

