Substrates	Glucose (Serum) Creatinine Bilirubin, Total Bilirubin, Direct Protein, Total Albumin Alpha glycoprotein acid C-Reactive Protein (Quant) Uric Acid Urea Cholesterol, total Triglyceride	X X X X X X X X X X X X X X X	X X X X X X X X X X X X X X
Electrolytes	Sodium Potassium Magnesium Calcium	X X X X	X X X X

Proprietary confidential information © 2018 Boehringer Ingelheim International GmbH or one or more of its affiliated companies

Table 5.2.3: 1 Routine laboratory tests (cont.)

Functional lab group	BI test name [comment/abbreviation]	A	B
Urinalysis (Stix)	Urine Nitrite (qual) Urine Protein (qual) Urine Glucose (qual) Urine Ketone (qual) Urobilinogen (qual) Urine Bilirubin (qual) Urine RBC/Erythrocytes (qual) Urine WBC/Leucocytes (qual) Urine pH	X X X X X X X X X	X X X X X X X X X
Urine sediment (microscopic examination if erythrocytes, leukocytes nitrite or protein are abnormal in urine)	Only positive findings will be reported (for instance, the presence of sediment bacteria, casts in sediment, squamous epithelial cells, erythrocytes, leukocytes)		

A: parameters to be determined at Visit 1 (screening examination)

B: parameters to be determined at Visit 2, Day -1, Day 2 and Day 6, and at Visit 3 (end-of-trial examination)

The tests listed in Table [5.2.3: 2](#) are exclusionary laboratory tests that may be repeated as required. The results will not be entered in the CRF/database and will not be reported in the CTR. Except for drug screening, it is planned to perform these tests during screening only. Drug screening will be performed at screening and on Day -1 of the treatment period.

To encourage compliance with alcoholic restrictions, an alcohol test in urine will be performed at screening and on Day -1 prior to the treatment period, and may be repeated at any time during the study at the discretion of an investigator or designee. The results will not be included in the CTR.

The laboratory tests listed in Tables [5.2.3: 1](#) and [5.2.3: 2](#) will be performed at the safety laboratory of

. The drug and alcohol screening tests will be performed using the ADVIA Chemistry XPT system.

Laboratory data will be transmitted electronically from the laboratory to the trial site.

Table 5.2.3: 2 Exclusionary laboratory tests

Functional lab group	Test name
Drug screening (urine)	Amphetamine/MDA Barbiturates Benzodiazepine Cannabis Cocaine Methadone Methamphetamines/MDMA/XTC Opiates Phencyclidine Tricyclic antidepressants Alcohol

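### Does the shorter fast required for the Day -1 laboratory baseline call for an added comparison with screening for glucose and triglyceride?

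*SAP*

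**What the plan says.** **Baseline.** SAP 6.7 applies a single rule to all parameters: "The last non-missing value determined prior to the first study drug administration will be defined as baseline".

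**Laboratory schedule.** Footnote 1 of the protocol Flow Chart places a laboratory panel at screening: "Screening procedures include physical examination, check of vital signs, ECG, safety laboratory (including drug screening". The note to Table 5.2.3: 1 gives the later samples: "B: parameters to be determined at Visit 2, Day -1, Day 2 and Day 6, and at Visit 3 (end-of-trial examination". The Day 1 pre-dose row of the Flow Chart marks PK, ECG and vital signs but no safety laboratory. Admission on Day -1 is planned for 14:00, and the Day 2 and Day 6 visits for 08:00, in a column headed "Approximate clock time of actual day".

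**Fasting.** Protocol 5.2.3 requires that subjects have "fasted for at least 4 h (at admission on Day -1, only) or at least 10 h (all other time points". It adds an exception: "Overnight fasting is not required at the discretion of the investigator or designee for re-tests".

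**Analytes.** The Substrates group of Table 5.2.3: 1 comprises "Glucose (Serum) Creatinine Bilirubin, Total Bilirubin, Direct Protein, Total Albumin Alpha glycoprotein acid C-Reactive Protein (Quant) Uric Acid Urea Cholesterol, total Triglyceride".

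**Use of the baseline.** Protocol 7.3.4 and SAP 7.8.2 both report laboratory differences from baseline, descriptively. Neither plans a difference from screening.

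**The concern.** The one scheduled sample with the shorter required fast is the one that serves as baseline. Every scheduled post-dose laboratory difference then sets a sample taken after a fast of at least 10 h against one taken after a fast of at least 4 h. For Day 2 and Day 6 it also sets a morning sample against an afternoon one.

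This mismatch comes from the schedule and applies to every subject, so more subjects would not average it out. A single-arm trial has no control group from which a shared shift could be subtracted. If glucose or triglyceride moved in the same direction in all subjects, a reader of the change table could take a fasting effect for a drug effect, or miss a drug effect that fasting had offset. Screening falls under the 10 h rule, so a second difference taken from screening looks like a cheap repair.

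**Working it through.** The documents state no figure for this point, so there is none to reproduce. The check sets the schedule against the fasting rule and then asks what depends on the result.

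**1. Gap in required minimum fast** (Protocol 5.2.3, Flow Chart, Table 5.2.3: 1)

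| Sample | Planned time | Required minimum fast | Minus Day -1 | Minus screening |
|---|---|---|---|---|
| Screening (Day -21 to -2) | not stated | 10 h | – | – |
| Day -1 (baseline) | about 14:00 | 4 h | – | – |
| Day 2 | about 08:00 | 10 h | 10 - 4 = 6 h | 10 - 10 = 0 h |
| Day 6 | about 08:00 | 10 h | 6 h | 0 h |
| End of trial (Day 9 to 15) | not stated | 10 h | 6 h | 0 h |

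These are minimums. A subject who arrives on Day -1 after 10 h without food has no gap in practice. Comparison with screening does not guarantee equal fasts either: the Day 2 sample is planned 13 h after the 19:00 dinner (19:00 to 08:00) if nothing is eaten in between, while screening need only follow 10 h.

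**2. Clock time.** The nominal gap from Day -1 to Day 2 or Day 6 is 14:00 - 08:00 = 6 h. Protocol 6.1 allows ±180 min on the later days of Visit 2. With Day -1 held at exactly 14:00, the gap runs from 6 - 3 = 3 h to 6 + 3 = 9 h.

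**3. Number of differences.** Assume that glucose and triglyceride are the fasting-sensitive analytes and that data are complete.

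- All post-dose visits: 2 analytes × 3 visits × 6 subjects = 36. With the maximum of 8 subjects: 2 × 3 × 8 = 48.
- The residual effect period is 7 × 24 h from dosing on Day 1, so it ends on Day 8. Only Day 2 and Day 6 fall within it: 2 × 2 × 6 = 24, or 2 × 2 × 8 = 32 with 8 subjects.

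The upper counts are unlikely to be reached in full. Subjects 7 and 8 enter only to replace subjects who vomited or dropped out, and a dropout may miss laboratory visits.

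In the text available here, the marks in the Substrates row do not line up with the tests. Both analytes are read as measured at every visit because column B shows no dash, unlike the hormone row.

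**4. What depends on these differences**

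- Hypothesis tests: none on safety data (Protocol 7.3.4).
- Clinical significance: judged by the investigator or settled at the report planning and database lock meeting, without automated flags (SAP 7.8.2).
- Adverse events of special interest: hepatic injury is defined by multiples of the upper limit of normal, and the other categories are infections (Protocol 5.2.6.1.4). None uses glucose, triglyceride or a change from baseline.
- Reference-range comparison, values over time and individual listings: none uses the baseline (Protocol 7.3.4; SAP 7 and 7.8.2).
- Primary AUC analysis: unaffected.

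**5. What an added block would supply.** SAP 7 gives N, mean, SD, minimum, median and maximum for continuous variables. If the by-visit table shows screening and data are complete, the mean difference from screening is the difference of two displayed means. Only the SD, minimum, median and maximum of the paired differences would be new, and with 6 to 8 subjects these can be worked out from the listings.

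**The case for a change.** The best case for acting is that the facts are right, the remedy costs one sentence and a small table block from data already collected, and nothing in SAP 6.7 or 7.8.2 warns the reader that baseline had a different fasting requirement. The spread of the paired differences also cannot be recovered from summary means.

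That much stands. It is weakened by what screening would bring as a comparator:

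- It lies 2 to 21 days before dosing and has no stated clock time, so it is less recent than Day -1 and not clearly closer in time of day.
- Its values feed eligibility through exclusion criterion 3, "Any laboratory value outside the reference range that the investigator considers to be of clinical relevance", so regression to the mean is possible.
- If a screening value prompted a re-test, neither choice is clean. The scheduled value is the one that was questioned, and the re-test may be exempt from overnight fasting.

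A second column would exchange one possible distortion for others of equally unknown size. SAP 7.8.2 also bases laboratory displays on a sponsor standard (SAP reference 9) that is not available here and may already include this comparison.

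**Conclusion.** No change to the plan is needed. The observation is correct within limits: for scheduled samples, the laboratory baseline carries a required minimum fast 6 h shorter than any post-dose sample, and for the planned 6 subjects this touches 36 descriptive differences, 24 within the residual effect period. Those differences may, not must, partly reflect fasting.

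The baseline rule is clear, can be carried out as written, and uses the last value before dosing. The shorter Day -1 fast is an explicit protocol choice and contradicts nothing in the SAP. The extra comparison would inform no decision, would largely repeat what the listings and by-visit summaries already give, and would rest on a comparator with its own weaknesses. Analysts can state the Day -1 fasting requirement and planned time in a table note when they report, without amending the SAP.

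This conclusion assumes that glucose and triglyceride are the relevant analytes, that both are measured at every visit, and that data are complete. The size of any fasting effect is unknown. No conclusion of the trial depends on it.

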7. PLANNED ANALYSIS

The format of the listings and tables will follow the BI guideline "Reporting of clinical trials and project summaries" ([5](#)).

The individual values of all subjects will be listed. Listings will generally be sorted by dose group, subject number and visit (if visit is applicable in the respective listing). AE listings will be sorted by assigned treatment (see [Section 7.8.1](#) below for details). The listings will be contained in Appendix 16.2 (SDL) of the CTR.

The following standard descriptive statistical parameters will be displayed in summary tables of continuous variables:

N	number of non-missing observations
Mean	arithmetic mean
SD	standard deviation
Min	minimum
Median	median
Max	maximum

For plasma concentrations as well as for all PK parameters the following descriptive statistics will additionally be calculated:

CV	arithmetic coefficient of variation
gMean	geometric mean
gCV	geometric coefficient of variation

For PK parameters the following descriptive statistics will additionally be calculated:

P10	10 th percentile
Q1	1 st quartile
Q3	3 rd quartile
P90	90 th percentile

The data format for descriptive statistics of plasma concentrations will be identical to the data format of the respective concentrations. The descriptive statistics of PK parameters will be calculated using the individual values with the number of decimal places as provided by the evaluation program. Then the individual values as well as the descriptive statistics will be reported with three significant digits in the CTR.

Tabulations of frequencies for categorical data will include all possible categories and will display the number of observations in a category as well as the percentage (%) relative to the respective treatment group. Percentages will be rounded to one decimal place. The category missing will be displayed if and only if there actually are missing values. Percentages will be based on all subjects in the respective subject set whether they have non-missing values or not.

7.1 DEMOGRAPHIC AND OTHER BASELINE CHARACTERISTICS

Only descriptive statistics are planned for this section of the CTR. These will be based on the TS.

7.2 CONCOMITANT DISEASES AND MEDICATION

Concomitant diseases will be coded according to the most recent version of MedDRA. Concomitant medication will be coded according to the most recent version of the World Health Organisation – Drug Dictionary.

Only descriptive statistics are planned for this section of the CTR based on the TS.

A medication will be considered concomitant to a treatment, if it

- is ongoing at the time of first administration of the respective treatment or
- starts within the analysis phase of the respective treatment (see [Section 6.1](#) for a definition of treatments and analysis phases).

